3.3.1 Potential Risks

The main risk associated with the study is the possibility that confidential information obtained during the study will be disclosed given the association of a medical disease and pain symptoms. Patient names and other identifying information do not appear on research records. For patients the iCanCope-NF must enter a unique id and passcode for access. All processes of obtaining information via Qualtrics, or iCanCope-NF will utilize proper data security methods to minimize any risks of for potential loss of confidentiality. **3.3.2 Potential Benefits**

We expect individuals with NF1 utilizing the iCanCope program to have decreased pain severity and interference if they regularly engage in the program. In addition, due to the added contingency management, we expect to see differences between the intervention groups (*iCanCope-NF* and *iCanCope-NF +CM*). By adding contingencies to increased

engagement the CM grouping should have more improvements in pain intensity and pain interference in addition to current iCanCope processes. If we demonstrate initial feasibility and preliminary impact a definitive RCT will be conducted.

4.1 Hypothesis

We hypothesize that by customizing the CBT and the MBAA in the mobile application for adults with NF1, individuals will engage regularly, thus acquiring a new set of skills to facilitate their own pain self-management, while pain will decrease.

4.2 Primary Objective

To evaluate whether the *iCanCope-NF* program will reduce pain (pain severity and pain interference) in adults with NF1.

4.3 Secondary Objectives (if applicable)

n/a

5.1 General Design Description

A 1x3 pilot randomized control trial (RCT) (*iCanCope-NF*, *iCanCope-NF* +Contingency Management (CM), Control Group) will be conducted with 108 adults with NF1 who suffer from pain.

5.1.1 Study Date Range and Duration

We predict the pilot RCT to take 18 months to complete (February 1, 2021 to August 2022). The patient networks that we are recruiting from have over 25000 adults across both groups. A conservative estimate of 20% of individuals should be within the appropriate age criterions (~5000). Given that we are seeking to fulfill 36 in each group for a total of 108 for the Pilot RCT and taken in account of a conservative 20% refusal rate. We should not encounter an issue with total number of individuals enrolled within the study within the time frame.

5.1.2 Number of Study Sites

There will be three study sites for this study: Yale School of Medicine, Connecticut Children's Hospital (Hartford, CT), and The Hospital of Sick Children (Toronto, Canada).

Yale School of Medicine: The PI will run the entire clinical trial through Yale School of Medicine. All potential participants will be recruited, consented, orientated to a treatment group (if applicable).

Connecticut Children's Hospital (Hartford, CT): will consult but will not have access to the PHI data. There will be no active recruitment or enrollment at the Connecticut Children's Hospital.

The Hospital of Sick Children (Toronto, Canada): will host the server of the iCanCope and the dashboard of the server but will not see any personal PHI. There will be no active recruitment or enrollment at the Hospital of Sick Children. *[name] (University of Toronto/University Health Network) will oversee the development of the ICC NF app and ensure that [name] and the Yale research team receives an intervention that can be trialed with their patient population. She will provide ongoing guidance and support of the technical requirements for the project, including the maintenance and tier 2 technical support*

of the ICC NF app through the trial. She will also lead on the development of the contingency management dashboard used by [name] research team to monitor engagement with the ICC NF app. [name] academic contributions will involve participating in regular investigator meetings on clinical trial progress and supporting [name] with data analysis, interpretation, and manuscript preparation. [name] will not have access to any identifiable data.,

5.2 Outcome Variables

5.2.1 Primary Outcome Variables

Primary Outcome Measure:

1. Engagement Activity

Total minutes logged on the mobile application will be evaluated between the two groups using the mobile application.

[Time Frame: through the completion of the study, on average 4 months.]

2. Pain Severity

A comparison within groups change of pain severity measured by the Brief Pain Inventory-Short Form. Respondents rate items on a 0-10 scale to indicate the pain severity and interference, and the total score is the mean of each subfactor. The higher the score indicates more severity and interference of pain.

[Time Frame: through the completion of the study, on average 4 months.]

3. Pain Interference Index

A comparison within groups change of pain interference measured by the Pain Interference Index Scale. Respondents rate items on a 0-6 scale to indicate how much pain has interfered with various activities, and the total score is the mean of the six items. Where 6 indicates high interference.

[Time Frame: through the completion of the study, on average 4 months.]

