5.2.2 Secondary and Exploratory Outcome Variables (if applicable)

Secondary Outcome Measures:

1. Treatment Services Review what are perceptions of satisfaction across groups exposed to the iCanCope mobile application using an The Treatment Services Review (TSR) [Time Frame: through the completion of the study, on average 4 months.]
2. Anxiety comparison within change of generalized anxiety measured by the generalized anxiety disorder scale (GAD-7). After reading each statement, one of four choices are provided and respondents can select one response (1=not at all sure, 2=several days, 3=over half days, 4=nearly every day). Each column is then added, and a total score is obtained, with scores falling into four levels of anxiety, including minimal (1-4), mild (5-9), moderate (10-14), and severe (15-21)[Time Frame: through the completion of the study, on average 4 months.]

3. Sleep functioning comparison within change of sleep quality measured by the PROMIS Sleep inventory. The higher the total score, the more severe the symptom. Total scores less than 24 suggest no to slight sleep disturbance, 24-28 suggest mild disturbance, 29-38 moderate disturbance, and greater than 38 severe sleep disturbance [Time Frame: through the completion of the study, on average 4 months.]
4. Short Form/Quality of Life the Short form survey 20- will measure quality of life across 8 subscales on respondent burden (Physical Functioning, Role-Physical, Bodily Pain, General Health, Vitality, Social Functioning, Role-Emotional, and Mental Health). Scores were transformed linearly to 0-100 scales, with 0 and 100 assigned to the lowest and highest possible scores, where high value indicated better functioning. [Time Frame: through the completion of the study, on average 4 months.]

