5.3.2 Eligibility Criteria/Vulnerable Populations

Patients will be included in the study if they meet the following inclusion criteria:

- 1) adults older than age of 18
- 2) diagnosis a diagnosis of NF1;
- 3) permanently reside in the United States and
- 4) have pain interference aggregate scores of three or more in the last two weeks using the Brief Pain Inventory-Short Form (BPI-SF) scale.

Patients will be excluded if they: 1) have an undiagnosed case of NF1; 2) have documented major co-occurring psychiatric disease; 3) have moderate to severe cognitive deficits; or 4) have depression assessed using the Patient Health Questionnaire (PHQ-9) or anxiety assessed using the Generalized Anxiety Disorder scale (GAD-7) greater than or equal to the appropriate thresholds (10=mild major depression; 5=mild severe anxiety).

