iCanCope-NF & CM Group: In addition to the *iCanCope-NF* activities outlined above, individuals will be rewarded with incentives such as points that are redeemable for prize-based gift card vouchers.[i] (#_edn1) Points will be accrued through access to new sections, daily check-ins, and engagement of the mobile application. Based on research, the total amount of money that can be earned by the patient over the course of the two months is 50 dollars USD. Individuals who are only randomized in the ICC-CM condition earn from \$1 to \$5 dollar amazon gift card per week for eight weeks (based on their usage). With an additional \$10 dollar gift card, if they check in every day. The total of the incentives can reach up to 50 dollars.

Control Group: The control group is designed to assess for potential effects on outcomes of time, attention, during the study. In addition to usual care, participants will be required to complete baseline and follow-up assessments similar to that of the intervention groups. They will be given that patient education, through preapproved flyers and information found from national websites regarding pain management, but no self-management strategies or opportunities for social support. They will not have access to the mobile application during the course of experiment; however, the control group will be offered the full *iCanCope-NF* program following the trial (T2) for a period of 2 months after the study is over.

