6.1.2 Method of Assignment/Randomization

Participants will be randomized to one of the three conditions using an urn randomization algorithm which modifies ongoing randomization probabilities based on prior group composition groups, and controls for other predictive factors. This process greatly reduces experimenter bias and other internal validity threats to integrity. Gender be the only variable

that will be attempted to controlled for to ensure equal representation across the groups within the urn randomization using stratification.

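### Pain is the primary objective and a primary outcome, but it is worded as within-group change, no primary analysis is assigned to it, and the comparison with control is only secondary and loosely specified

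*Combined protocol and SAP*

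**What the plan says.** Section 4.2 (and the Synopsis) states the primary objective as whether the "program will reduce pain (pain severity and pain interference) in adults with NF1". Section 5.2.1 lists three primary outcomes. The first is a between-group measure: "Total minutes logged on the mobile application will be evaluated between the two groups using the mobile application". The second is "A comparison within groups change of pain severity measured by the Brief Pain Inventory-Short Form" and the third is "A comparison within groups change of pain interference measured by the Pain Interference Index Scale". The time frame for all three is study completion, about four months on average, with no visit named.

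Section 6.4.3.1, which repeats text from 6.4.3, treats as primary the feasibility counts, acceptability and satisfaction, and engagement. It names neither the BPI-SF nor the Pain Interference Index. Section 6.2.1 likewise makes feasibility the primary research question and the pain comparison with control a secondary one. Satisfaction, primary in 6.4.3.1, is a secondary outcome in 5.2.2 ("perceptions of satisfaction across groups exposed to the iCanCope mobile application").

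Section 6.4.3.2 holds the only pain comparison with control. It is secondary question 1, iCanCope-NF against control at T2, using an estimating-equation approach to scores plus multilevel logistic models for the probability of unspecified pain levels. Secondary question 2 compares pain between the two app arms only.

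**The concern.** A within-arm change mixes any effect of the app with everything else that moves pain scores over eight weeks. Two features of this trial make that more than a formality. Participants must "have pain interference aggregate scores of three or more in the last two weeks" on the BPI-SF, so scores on that scale, and on scales correlated with it, tend to fall on re-measurement without treatment. And the protocol states why it has a control arm: "The control group is designed to assess for potential effects on outcomes of time, attention, during the study". A within-arm primary outcome makes no use of that arm.

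The second issue is that the declared primary outcomes and the declared primary analyses disagree. Two of the three primary outcomes have no analysis assigned to them under 6.4.3.1. Which pain result is the headline (pre-post change, the estimating-equation contrast, or a logistic model with a cut-point chosen later) can be settled after the data are seen. Section 6.4.1 promises corrections for multiple tests but names no method, so it does not limit that choice. The trial is meant to inform a definitive RCT, so a misread pain signal would carry forward.

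**Working it through.** **1. The passages side by side**

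| Section | What is primary | Status of pain |
|---|---|---|
| 4.2 | Pain reduction | Primary objective |
| 5.2.1 | Engagement, BPI-SF severity, Pain Interference Index | Primary, within-group change |
| 6.2.1 | Feasibility | Secondary, v control at T2 |
| 6.4.3 and 6.4.3.1 | Feasibility, satisfaction, engagement | Not named |
| 6.4.3.2 | – | Secondary: iCanCope-NF v control; CM v no CM |

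This conflict needs no assumption. There is no stated pain figure to reproduce: the sample-size section gives 36 per group but no test, effect size, SD or power.

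**2. Regression to the mean with no treatment effect**

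From the documents: 36 per arm, entry at interference ≥3. Assumed: population mean μ, SD σ, test-retest correlation r, severity–interference correlation ρ.

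For a normal score with μ = 3, the mean excess among those at or above 3 is 0.798σ. With σ = 2.5 that is 1.995. Expected falls:

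- Entry scale: (1 − r) × 1.995 = 0.3 × 1.995 = 0.60.
- Severity: ρ(1 − r) × 1.995 = 0.30 at ρ = 0.5 and 0.42 at ρ = 0.7.

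Simulation of 3,000 two-arm trials per scenario, with scores clipped to 0–10, gives slightly smaller falls:

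| Case | Mean fall | Paired test p < 0.05 per arm |
|---|---|---|
| Severity, μ 3, σ 2.5, r 0.7, ρ 0.5–0.7 | 0.28–0.39 | 14–24% |
| Entry scale (BPI interference), same inputs | 0.59 | 48% |
| Severity, μ 2–5, σ 2–2.5, r 0.6–0.8, ρ 0.5–0.7 | – | 6–56% |
| Severity, μ = 5 only | – | 6–10% |

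The between-arm test rejects in 4–6% throughout, as it should.

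**3. Any shared improvement**

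If every arm improves by the same standardised change, a paired t test at n = 36 has noncentrality 6 × change. For changes of 0.2, 0.3 and 0.5 it is significant in p = 21%, 42% and 83% of arms. The chance that at least one app arm is significant and control is not is [1 − (1 − p)²](1 − p), which is 30%, 39% and 16%. One valid between-arm test gives 5%.

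**4. Zero-coding**

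Section 6.4.5 codes missing data as zero, which on a pain scale means no pain. If 20% of T2 scores are set to 0, the mean falls by 0.20 × the baseline mean: 0.8 at a mean of 4 and 1.0 at 5. By simulation (6,000 arms of 36, SD 1.5–2, r 0.6–0.8), a paired test is significant in 49–78% of arms with no true change.

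**5. What a between-arm contrast delivers at 36 per arm**

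Two-sided noncentral t; baseline adjustment multiplies the variance by 1 − r².

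- Unadjusted power at an assumed d = 0.3 and 0.5: 24% and 55%.
- Adjusted at d = 0.5, r = 0.5–0.7: 68–83% at alpha 0.05, and 43–63% at alpha 0.05/5 = 0.01.
- 95% CI half-width: 1.994 × √(2/36) = 0.47 SD unadjusted; × √(1 − r²) gives 0.41 SD at r = 0.5 and 0.34 SD at r = 0.7.

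**The case against.** The strongest case for the plan has four parts.

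- **A pain analysis may be intended.** Section 6.4.3.1 mentions an ANOVA of proportional changes and a Cox regression of pre and post. Neither names an outcome, both sit under the feasibility question, and the Cox model has no defined event. They could be meant for pain, but the text does not say so. The wording of outcomes 2 and 3 could also mean comparing changes across arms; the first outcome, however, is stated explicitly as between groups, and on either reading no analysis is clearly assigned to pain.
- **The control comparison exists and may cover both app arms.** The phrase iCanCope-NF program can be read to include the CM arm. That is a fair ambiguity: a CM-versus-control pain contrast is at most implied. A pooled contrast (72 v 36) would have 68% power at d = 0.5 unadjusted, against 55% for a single arm, but the plan does not state one.
- **The percentages rest on assumptions.** This stands. No paired test is named in the plan. A population mean of 3 is not documented, and at a mean of 4 severity gives only about 7–17%. The 48% belongs to the entry scale, which is not a declared primary outcome, and the Pain Interference Index was not simulated. Because 36 is already the number after attrition, the zero-coding example counts attrition twice; using the enrolled number would raise the percentage. Section 6.4.5 does not say explicitly that zero-coding applies to pain scores.
- **It is a pilot.** A pilot may make feasibility primary. It should then say so everywhere, which this protocol does not.

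**Conclusion.** The concern holds and should be fixed before analysis. The contradiction among 4.2, 5.2.1, 6.2.1 and 6.4.3.1 is on the page and depends on no assumption: the primary objective has no clearly assigned primary analysis, and its outcomes are worded so that an uncontrolled pre-post fall could satisfy them.

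The size of the resulting error is much less certain. If the population mean is well above the entry threshold, regression to the mean alone is a small problem. If it is near or below the threshold, or if all arms improve for other reasons, or if missing pain scores are set to zero, a within-arm test would often be significant for an app with no effect. Under the same no-effect regression-to-the-mean assumptions, the between-arm test keeps its error rate near 5%.

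**What to change.** Choose one of two routes and apply it consistently.

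**Route A: pain stays primary.**

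- In the Synopsis and 5.2.1, define outcomes 2 and 3 as the between-arm difference in score at T2, each app arm against control (or a stated pooled contrast). Set the time frame to T2 in place of the four-month wording.
- In 6.4.3.1, specify ANCOVA or a mixed model on the numeric score, with baseline score and gender as fixed covariates, reported as an estimate with 95% CI. Gender is the urn factor in 6.1.2 ("Gender be the only variable"). Name the covariates in 6.4.4 and do not select them by baseline tests.
- Report within-arm change as descriptive only.
- State the multiplicity rule. One option is Holm over five tests: engagement between the app arms, and two pain outcomes for each of two app arms against control.
- For pain, replace zero-coding with a likelihood-based mixed model or multiple imputation. Section 6.3.6 does not survey early leavers. Either invite them to the T2 survey unless consent is withdrawn, or state the missing-data assumption and add a sensitivity analysis.

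**Route B: feasibility is the sole primary.** Make pain secondary in the Synopsis, 4.2, 5.2.1, 6.2.1 and 6.4.3.1, still defined as a contrast with control, and give satisfaction the same status in 5.2.2 and 6.4.3.1.

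The between-arm definition, or Route B, is essential. The particular Holm family and the added follow-up of early leavers are optional.

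**Cost.** Mostly wording, through an IRB amendment; surveying early leavers adds some work. The headline may look weaker, because the control arm's improvement is subtracted and precision at 36 per arm is limited, particularly at the first Holm step.

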5.2.2 Secondary and Exploratory Outcome Variables (if applicable)

Secondary Outcome Measures:

1. Treatment Services Review what are perceptions of satisfaction across groups exposed to the iCanCope mobile application using an The Treatment Services Review (TSR) [Time Frame: through the completion of the study, on average 4 months.]
2. Anxiety comparison within change of generalized anxiety measured by the generalized anxiety disorder scale (GAD-7). After reading each statement, one of four choices are provided and respondents can select one response (1=not at all sure, 2=several days, 3=over half days, 4=nearly every day). Each column is then added, and a total score is obtained, with scores falling into four levels of anxiety, including minimal (1-4), mild (5-9), moderate (10-14), and severe (15-21)[Time Frame: through the completion of the study, on average 4 months.]

3. Sleep functioning comparison within change of sleep quality measured by the PROMIS Sleep inventory. The higher the total score, the more severe the symptom. Total scores less than 24 suggest no to slight sleep disturbance, 24-28 suggest mild disturbance, 29-38 moderate disturbance, and greater than 38 severe sleep disturbance [Time Frame: through the completion of the study, on average 4 months.]
4. Short Form/Quality of Life the Short form survey 20- will measure quality of life across 8 subscales on respondent burden (Physical Functioning, Role-Physical, Bodily Pain, General Health, Vitality, Social Functioning, Role-Emotional, and Mental Health). Scores were transformed linearly to 0-100 scales, with 0 and 100 assigned to the lowest and highest possible scores, where high value indicated better functioning. [Time Frame: through the completion of the study, on average 4 months.]
5. Chronic pain acceptance Chronic Pain Acceptance Questionnaire-Revised (CPAQ-Revised) 20-item scale designed to measure acceptance of pain. The acceptance of chronic pain is thought to reduce unsuccessful attempts to avoid or control pain and thus focus on engaging in valued activities and pursuing meaningful goals will be measured across all groups. The items on the CPAQ are rated on a 7-point scale from 0 (never true) to 6 (always true). To score the CPAQ, add the items for Activity engagement and Pain willingness to obtain a score for each factor. To obtain the total score, add the scores for each factor together. Higher scores indicate higher levels of acceptance [Time Frame: through the completion of the study, on average 4 months.]
6. psychological inflexibility Psychological Inflexibility in Pain Scale (PIPS) 16-item scale used to assess psychological inflexibility (i.e. avoidance, acceptance, fusion, values orientation, dirty discomfort) in people with chronic pain will be measured across all groups. Respondents are asked to rate items on a 7-point scale that ranges from 1 (never true) to 7 (always true). Higher scores indicate greater levels of psychological inflexibility. [Time Frame: through the completion of the study, on average 4 months.]

Other Pre-specified Outcome Measures:

1. Mindfulness based alternative approaches (MBAA) Do individuals with NF1 utilize the MBAA more readily because they are on the mobile application, via Five Facet Mindfulness Questionnaire. 39-item self-completed questionnaire measuring the five facets of mindfulness: Observing (8 items), Describing (8 items), Acting with awareness (8 items), Non-judgmental (8 items), and Non-reactive (7 items). Participants rated the items on a five-point Likert scale (1 = never or very rarely true to 5 = very often or always true), each facet score ranges from 8 to 40, except for the non-reactive facet which ranges from 7 to 35. [Time Frame: through the completion of the study, on average 4 months.]

5.3 Study Population

A convenience sample of 108 adults with NF1 above the age of 18 will be recruited through mail merge and emails, Internet advocacy web forums (NF Northwest and NF Network).

5.3.1 Number of Participants

A convenience sample of 108 adults with NF1 aged 18-34 will be recruited through mail merge and emails, Internet advocacy web forums (NF Network, NF Northeast: see letters of support).

Power Analysis: An a priori power analysis conducted through G*Power (Universität Kiel, v. 3.1.9.2) estimated a conservative sample size analysis for the RCT. We are expecting a total of 140 participants, given the length of the trial, we estimate 20% attrition rate of the final sample, giving us a total sample of (n=36) per group, for a final sample size of 108. The power analysis is based on previously utilized research in which estimated effect sizes ranged from 20 to 40 individuals per group (52). We will attempt to enroll equal numbers of male and female individuals to evaluate gender differences through urn randomization process.

52. Hancock, G. R. and R. O. Mueller, Eds. (2010). *The Reviewer's Guide to Quantitative Methods. Power Analysis*. New York, NY, Routledge.

